6.5 Vital signs – definition of clinically notable and relevant values

The following table shows the clinical notable criteria for vital signs.

Table 6-5-1 Vital signs - clinical notable values

Vital sign parameter (unit)	Lower bound of clinically notable range	Upper bound of clinically notable range
Notable value considering newly occurring or worsening cases		
Systolic blood pressure (mmHg)	< 75	> 200
Diastolic blood pressure (mmHg)	< 40	> 115
Pulse rate (bpm)	< 40	> 130
Notable change from baseline		
Systolic blood pressure (mmHg)	≤ 90 and decrease from baseline by ≥ 20	≥ 180 and increase from baseline by ≥ 20
Diastolic blood pressure (mmHg)	≤ 50 and decrease from baseline by ≥ 15	≥ 105 and increase from baseline by ≥ 15
Pulse rate (bpm)	≤ 50 and decrease from baseline by ≥ 15	≥ 120 and increase from baseline by ≥ 15
Weight (kg)	Decrease ≥ 7% from baseline	Increase ≥ 7% from baseline

6.6 Statistical methodology and assumptions

SAS codes for all statistical methodology described in this section will be included in Table, Figure, Listing (TFL) Shells as programming note.

6.6.1 Multiple imputations for primary and secondary variables

The imputation and analysis of primary and secondary variables will be implemented using the “five macros” available from www.missingdata.org.uk (for a full description see Carpenter et al (2013)). The purpose and activities of each of the five macros is described below.

Part1A declares the parameter estimation model and checks consistency with the input dataset. It builds a master dataset which holds details of the current job and also builds indexes for the classification variables, which may be either numeric or character.

Part1B fits the parameter estimation model using the MCMC procedure and draws a pseudo-independent sample from the joint posterior distribution for the linear predictor parameters and the covariance parameters.

Part2A calculates the predicted mean under MAR, and under MNAR for each subject based on their withdrawal pattern once for each draw of the linear predictor parameter estimates. The choice of MNAR is controlled by the method used, which may vary from subject to subject.

Part2B imputes the intermediate missing values using MAR and the trailing missing values using MNAR, by deriving the conditional distribution for the missing values conditional on the observed values and covariates, using the appropriate sampled covariance parameter estimates.

Part3 carries out a univariate ANOVA analysis at selected time points usually based on the same covariates as the parameter estimation model. It then combines the least-squares means and their differences using the MIANALYZE procedure to provide final results.

This is example code to implement the primary analysis:

```
%part1A(Jobname=fev1
,Data=RE
,Subject=subjid
,Response=aval
,Time=visit
,Treat=trt01pn
,Covbytime= basefev basescore basesaba
,Catcov=stratum
,
);
```

Where subjid = subject identifier

aval = change from baseline in FEV1 value at visit during the treatment epoch

visit = treatment period visit number

trt01pn = planned treatment

basefev = baseline FEV1 value

basescore = baseline daytime asthma symptom score

basesaba = baseline total daily SABA use

stratum = randomization strata (patient age (<18 years or \geq 18 years), use or not use a second asthma controller at study entry, region)

```
%part1B(Jobname=fev1
,Ndraws=1000
,thin=750
,seed=12345
);
%part2A(Jobname=fev1_J2R
,inname=fev1
,methodV=Mymethod
,refV=Myreference
);
```

where Mymethod = Method used to impute missing data: J2R for QAW patients who discontinued treatment and MAR otherwise. Myreference = Placebo

```
%part2B(Jobname=fev1_J2R
,seed=832216);
```

```
%part3(Jobname=fev1_J2R
,ANTreat=trt01pn
,label=Mixed MAR and J2R);
```

Results will be presented as Least Squares Means (LSM) and standard errors (SE) for treatment effects and LSM, SE, associated two-sided 95% confidence interval, and two-sided p-value for all relevant treatment contrasts.

6.7 Rule of exclusion criteria of analysis sets

Subject classification in the analysis sets (FAS, Safety, Per Protocol, SCR, and RAN) will be based on protocol deviation specifications and non-protocol deviation classification criteria as following.

Table 6-7-1 Protocol deviations that cause subjects to be excluded

Deviation ID	Description of Deviation	Exclusion in Analyses
INCL01a	Informed consent was not obtained	SCR, RAN, FAS, PPS, SAF
INCL02	Age < 12 years	PPS
INCL03	No current diagnosis of Asthma of at least 6 months prior to V1	PPS
INCL05a	For patients aged >= 18 years, % predicted FEV1 was not <= 85% at both V1 & V101	PPS
INCL05b	For patients aged 12 years to <18 years, % predicted FEV1 was not <= 90% at V1 & V101	PPS
INCL05c	Spirometry done for assessing study eligibility is not meeting ATS/ERS criteria for acceptability or repeatability.	PPS
INCL08	Reversibility not demonstrated before randomization	PPS
EXCL01	Other investigational drug used within 30 days or within 5 half-lives prior to Screening	PPS
EXCL10b	Smoking history of greater than 10 pack years	PPS
EXCL11	Patient had an asthma exacerbation requiring systemic corticosteroids, hospitalization, or emergency room visit within 6 weeks prior to Visit 1	PPS

Deviation ID	Description of Deviation	Exclusion in Analyses
EXCL12	Patient had an asthma exacerbation requiring systemic corticosteroids, hospitalization or emergency room visit during the screening or placebo run-in periods.	PPS
EXCL13	Patients had respiratory tract Infection or asthma worsening within 4 weeks prior to V1.	PPS
COMD01	Prohibited asthma related ConMed during treatment epoch	PPS
COMD04	Permitted asthma related medication not taken as allowed under certain conditions during treatment epoch	PPS
COMD05	Baseline asthma medication or their dose was changed after Visit 1	PPS
OTH04	Patient randomized in error	PPS

Table 6-7-2 Subject Classification

Analysis Set	PD ID that cause subjects to be excluded	Non-PD criteria that cause subjects to be excluded
SCR	INCL01a,	NA
RAN	INCL01a	NA
FAS	INCL01a	Not in RAN; Randomized and no double-blind study drug taken
PPS	INCL01a,INCL02,INCL03, INCL05a,INCL05b,INCL05c, INCL08,EXCL01,EXCL10b, EXCL11,EXCL12, EXCL13,COMD01,COMD04 ,COMD05,OTH04	Not in FAS;
SAF	INCL01a	No double-blind study drug taken

7 Reference

[name] (2004). Asthma Control Questionnaire: Background, Administration and Analysis

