Key inclusion criteria	
 
• Patients must have a diagnosis of asthma (according to GINA 2016) for a period of at least 6 months prior to Visit 1.
 
• Patients who have been treated with: 
 
• Medium dose ICS, or
 
• High dose ICS, or
 
• Low dose ICS plus long-acting beta agonist (LABA), or
 
• Low dose ICS plus leukotriene receptor antagonist (LTRA), or
 
 
 

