	
 
• Medium dose ICS plus LABA.
 
 
for at least 3 months prior to Visit 1 and the doses have been stable for at least 4 weeks prior to Visit 1.
 
 
• For patients aged <math>\geq 18</math> years, FEV1 of <math>\leq 85\%</math> of the predicted normal value for the patient, after withholding bronchodilators at Visit 1 and Visit 101. For patients aged 12 to <math>< 18</math> years, FEV1 of <math>\leq 90\%</math> of the predicted normal value for the patient, after withholding bronchodilators at Visit 1 and Visit 101.
 
• Patients must have a daytime asthma symptom score (0 to 6 scale) of <math>\geq 1</math> per day during 4 of the last 7 days of the placebo run-in period.
 
• Patients must have a total daily SABA use <math>\geq 1</math> puff per day during 4 of the last 7 days of the placebo run-in period.
 
• Demonstrated reversible airway obstruction as determined by the central reader from the spirometry vendor at Visit 1 or Visit 101. Reversibility is defined as an increase of <math>\geq 12\%</math> and <math>\geq 200</math> ml in FEV1 approximately 10 to 15 minutes after administration of 400 mcg of salbutamol/albuterol (or equivalent). Spacer devices are permitted for administration of salbutamol/albuterol (or equivalent) during reversibility testing only. The Investigator or delegate may decide whether or not to use a spacer for the reversibility testing.             
 
• If reversibility is not demonstrated at Visit 1, reversibility will be attempted at Visit 101. If not achieved at Visit 101, one additional attempt to demonstrate reversibility is permitted within 4 days following Visit 101 in an ad-hoc visit to meet this eligibility criterion.
 
 
Review Visit 1 or Visit 101 or the one additional attempt reversibility result from overread by the spirometry vendor central reader prior to randomization.
 
 
• An asthma control questionnaire (ACQ) score <math>\geq 1.5</math> at Visit 199.
 

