#### **9.1 Analysis sets**

The screened set (SCR) will include all patients who provided informed consent.

The full analysis set (FAS) will include all randomized patients who received at least one dose of study drug. It was considered reasonable to limit the FAS to patients who took trial medication, because the decision on whether or not study drug is started will not be influenced by the treatment group assignment due to the effective treatment blinding procedures described in [Section 5.4](#). Following the intent-to-treat principle, patients will be analyzed according to the treatment they were assigned to at randomization.

The per-protocol set (PPS) will include all patients in the FAS without any major protocol deviations such as violation of major entry criteria or low compliance. Patients may also be considered censored for the PPS analysis at the time of major post-baseline protocol deviations. Major protocol deviations will be defined in the study specification document

prior to database lock and the un-blinding of the study. Patients will be analyzed according to the treatment they received.

The safety set (SAF) will include all patients who received at least one dose of double-blind study drug. Patients will be analyzed according to the treatment they received.

The analysis of the primary objective will be performed on the FAS. The PPS will be used for the supportive analysis of the primary and the secondary variables. The FAS will be used for the analysis of all other efficacy variables. The SAF will be used in the analysis of all safety variables.

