2.2 Analysis sets

The following analysis sets are defined:

- The screened set (SCR) will include all patients who provided informed consent.
- The randomized (RAN) set will consist of all patients who were assigned a randomization number, regardless of whether or not they actually received study medication. Patients in RAN will be analyzed according to the treatment they were randomized to.
- The Full Analysis Set (FAS) will consist of all randomized patients who received at least one dose of study medication. It was considered reasonable to limit the FAS to patients who took trial medication, because the decision on whether or not study drug is started will not be influenced by the treatment group assignment due to the effective treatment blinding procedures. Following the intent-to-treat principle, patients will be analyzed according to the treatment they were assigned to at randomization. The FAS will be used for the analysis of all efficacy endpoints, and for the summaries of patient disposition, demographic and baseline characteristics.
- The Per-Protocol Set (PPS) will include all patients in the FAS who did not have any major protocol deviations such as violation of major entry criteria. Protocol deviations will be defined in the data review plan document prior to database lock and the un-blinding of the study. Protocol deviations leading to exclusion from analysis sets are

defined in Section 6.7. Patients in the PPS will be analyzed according to the treatment they actually received. The PPS may be used for supportive analysis of the primary efficacy endpoint.

- The Safety Set (SAF) will consist of all patients who received at least one dose of double-blind study drug. Patients will be analyzed according to the treatment they received. The SAF will be used in the analysis of all safety variables. If due to a dispensing error a patient erroneously received any study treatment which is different from the randomized treatment, the patient will be analyzed according to the treatment they were randomized to.

Note that the set of patients included in the FAS and SAF are the same except that the SAF allows the inclusion of non-randomized patients who receive study drug in error.

In cases where an incorrect randomization stratum is entered in the IRT (interactive response technology), the corrected stratum information as per the CRF data will be used for reporting and analysis.

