2.3.2 Patient demographics and baseline characteristics

Demographics and baseline characteristics will be summarized by treatment group using the FAS set. Summaries will include age, gender, race, ethnicity, height, weight, BMI, pre- and post-bronchodilator FEV₁, percent predicted FEV₁, [REDACTED], FEV₁ reversibility, duration of asthma, number of asthma exacerbations in prior year, atopic asthma at entry into the study (Yes/No), smoking history (never/former), number of pack years, baseline ACQ-5, baseline AQLQ+12, [REDACTED], [REDACTED], and ICS use (alone, plus LABA, plus LTRA), ICS dose ranges (low, medium, high), [REDACTED] and daytime asthma symptom scores.

Background asthma therapy will be categorized into GINA steps and will be summarized at baseline. Background asthma therapy is defined as concomitant medication start date on or before Visit 1 and end date after Visit 1. Continuous variables will be summarized using

descriptive statistics (number of non-missing data, mean, standard deviation, median, first and third quartiles, minimum, and maximum) and categorical variables will be summarized in terms of the number and percentage of patients in each category including a category for missing data if any for the treatment group.

No statistical analyses will be provided for baseline comparability among the treatment groups.

In addition, the following categorizations of continuous variables will be done:

- Age: <18, 18 to <65, and ≥ 65 years;
- BMI: $\leq 30.0 \text{ kg/m}^2$ and $> 30.0 \text{ kg/m}^2$;
- Duration of asthma: < 1 year, 1 - 5 years, > 5 - 10 years, > 10 - 15 years, > 15 - 20 years, and > 20 years;
- Number of asthma exacerbations in prior year: 0, 1-2, 3, 4, ≥ 5
- pre-bronchodilator percent predicted FEV₁: $\leq 40\%$, $>40\% - \leq 50\%$, $>50\% - \leq 60\%$, $>60\% - \leq 70\%$, $>70\% - \leq 80\%$, $>80\%$
- ACQ-5: 1.5- < 2, 2 - < 2.5, ≥ 2.5 (< 1.5 will be added in case of protocol deviations)
- [REDACTED]

Derivation of the demographics and baseline characteristics

- BMI is calculated as: $\text{BMI (kg/m}^2\text{)} = \text{Weight (kg)} / [\text{Height (m)} * \text{Height (m)}]$
- Estimated number of pack years is calculated by the total years of smoking multiplied by cigarette packs smoked per day. This will be summarized as recorded on the eCRF. Smoking history in package years will be calculated as: (1 pack year = 20 cigarettes/day x 1 year or 10 cigarettes/day x 2 years).

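### The SAP's per-protocol exclusion list has no code for three inclusion criteria that mark uncontrolled asthma and none for low compliance, so the PPS is a weaker check on the FAS result than protocol 9.1 describes

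*SAP*

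**What the plan says.** Protocol 9.1 builds the PPS from FAS patients "without any major protocol deviations such as violation of major entry criteria or low compliance" and leaves the list of major deviations to be fixed before database lock and unblinding. SAP 2.2 repeats the definition but gives only major entry criteria as its example; low compliance is gone. It then points to one place for the operative list: "Protocol deviations leading to exclusion from analysis sets are" defined in section 6.7.

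The PPS row of Table 6-7-2 there holds 16 codes: seven INCL codes ("INCL01a,INCL02,INCL03, INCL05a,INCL05b,INCL05c, INCL08,EXCL01,EXCL10b" contains all of them), five EXCL codes (01, 10b, 11, 12, 13), COMD01, COMD04, COMD05 and OTH04.

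Protocol 3.2 says that the run-in establishes the level of asthma control from ACQ, reversibility, SABA use and daytime symptom score. SAP 2.3.2 provides for patients below the ACQ threshold: a category "< 1.5 will be added in case of protocol deviations". SAP 2.4.1.2 derives a compliance category below 80% but uses it only for a descriptive summary on the safety set.

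On the role of the PPS, protocol 9.4.4 commits to repeating the primary and secondary analyses on it. SAP 2.2 and 2.5.5 say only that the primary analysis may be repeated.

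**The concern.** A per-protocol analysis supports the FAS result because it removes patients who should not have been enrolled or did not take the drug as planned. If such patients stay in, the two sets become alike in composition, and agreement between them is partly built in.

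Here the uncoded criteria are not peripheral. Of the four run-in markers of control in protocol 3.2, only reversibility has a named PPS code. A patient randomised with an ACQ below 1.5, or below the symptom or SABA threshold, has no listed ground for removal unless OTH04 happens to apply. The same holds for a patient who took study drug irregularly, although the protocol names low compliance as a ground. At stake is the value of a supportive analysis, and the fact that the SAP narrows a protocol definition without saying so.

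**Working it through.** **Criteria against codes.** The protocol summary lists seven key inclusion criteria, numbered 3 to 9 in protocol 4.1.

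- 3, diagnosis: coded, INCL03 ("No current diagnosis of Asthma of at least 6 months prior to V1").
- 4, background regimen ("Patients who have been treated with" one of five listed regimens): no INCL04. COMD04 covers permitted asthma medication used outside its conditions, which points to protocol Table 5-1, and that table restates criterion 4. But COMD04 is limited to the treatment epoch and COMD05 to changes after Visit 1. Criterion 4 also requires 3 months of use and 4 weeks of stable dose before Visit 1; a failure of that history alone is not clearly caught. Exclusion criteria 25 and 27, which bear on the same point, have no code.
- 5, FEV1: coded, INCL05a to c (for example "For patients aged >= 18 years, % predicted FEV1 was not <= 85% at both V1 & V101").
- 6, symptom score ("Patients must have a daytime asthma symptom score (0 to 6 scale) of" at least 1 on 4 of the last 7 run-in days): no code.
- 7, SABA use: no code.
- 8, reversibility: coded, INCL08.
- 9, ACQ of at least 1.5 at Visit 199: no code.

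Count: 3 of 7 coded by name (3, 5, 8), 1 of 7 covered in part (4), 3 of 7 without a named code (6, 7, 9). Compliance codes: 0.

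**Declaration.** The visible bullets of SAP section 4 cover age derivation, shift tables, the TEAE window, an added responder analysis, analyses moved outside the CSR and similar items. None mentions PPS entry criteria or compliance. One bullet is blacked out, so this is a statement about the visible text only.

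**The plan's own figure.** The documents give no figure for the PPS. The stated power for the primary FAS analysis is 90.3% (112 mL, SD 380 mL, 15% discontinuation, 325 per arm). A two-sample closed form at two-sided 5%, giving all discontinuers zero effect as a stand-in for jump-to-reference, uses 112 × (1 − 0.15) = 95.2 mL and returns 89.1%. The other two rows of protocol Table 9-1 return 85.2% (stated 85.9) and 81.4% (stated 80.9). All three are within 2 points, and none depends on the PPS.

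**What retention could do (illustration only).** Let q be the share of patients who are uncoded violators and suppose, as an extreme, that the drug does nothing in them. If they are kept, the expected difference is 95.2 × (1 − q); if removed, it stays at 95.2 mL with fewer patients.

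- q = 1%: 94.2 mL, power 88.5% kept; 88.8% removed (321 per arm).
- q = 5%: 90.4 mL, 85.9% kept; 87.5% removed (308 per arm).
- q = 10%: 85.7 mL, 82.0% kept; 85.7% removed (292 per arm).
- q = 20%: 76.2 mL, 72.4% kept; 81.5% removed (260 per arm).

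The losses are 1.0, 4.8, 9.5 and 19.0 mL. If violators keep half the effect, each loss halves; if they respond fully, it is zero. For scale, the unadjusted standard error with 325 per arm is 380 × √(2/325) = 29.8 mL, so a 9.5 mL loss is 9.5/29.8 = 0.32 standard errors.

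**What the compliance measure sees.** SAP 2.4.1.2 divides days with intake by the days from Day 1 to the last known dose. A patient who takes every dose for 7 days and then stops scores 100 × 7/7 = 100%, although that is 7/84 = 8.3% of the planned 84 days. A cut at 80% finds irregular takers, not early discontinuers.

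**The case against.** The other side has real points.

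- *COMD04 reaches criterion 4.* This stands in part. A regimen outside Table 5-1 that continues into treatment would be caught, so a reader who counts four of the seven key criteria as unenforced goes too far.
- *OTH04 could catch the rest.* Criteria 6, 7 and 9 are settled at the end of run-in, on the day of randomisation, so a patient who fails one and is still randomised might be coded as randomised in error. The SAP gives OTH04 no scope, however. Since criteria 3, 5 and 8 have their own codes, it is unsafe to assume that OTH04 silently covers 6, 7 and 9. Overlapping codes are possible, so this is a matter of reading, not proof.
- *Protocol 9.1 only gives examples, and a key criterion in a summary is not declared to be a major one.* True, and the protocol sets no PPS compliance threshold. But low compliance is one of only two examples it names, and dropping it is a change that section 4 should record.
- *Violators should be few.* Protocol 5.3 requires all criteria to be confirmed before the IRT is contacted, and the ACQ category in SAP 2.3.2 is a contingency, not evidence that violators exist. This stands, but the same safeguard applies to criteria 3, 5 and 8, which still received codes.
- *The on-treatment MMRM in SAP 2.5.5 already looks at patients on drug.* It restricts data to the time on treatment. It removes neither ineligible patients nor irregular takers.

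**Conclusion.** The point holds as a gap in a supportive analysis. Three of seven key inclusion criteria have no named PPS code, one is covered in part, the protocol's low-compliance ground is absent, and the visible text of SAP section 4 declares none of this. The PPS is not purified for these violators and is a weaker check on the FAS result than protocol 9.1 describes.

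A reader might infer that the PPS fails to test the drug in uncontrolled asthma, or that the primary conclusion is at risk. The documents support neither. The objective is tested on the FAS, which keeps such patients by design. The SAP makes the PPS analysis optional, and under the eligibility check most PPS patients would still be eligible. Primary test, alpha and sample size do not change.

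The size of any dilution is unknown. The losses of 1.0 to 19.0 mL shown rest on assumed violator shares of 1 to 20% and an assumed zero effect in them; the documents give neither. The finding itself rests on the plain reading that OTH04 does not cover criteria 6, 7 and 9, and that the blacked-out bullet does not declare the change.

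**What to change.** Before unblinding:

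1. Add INCL06, INCL07 and INCL09 to Tables 6-7-1 and 6-7-2 as PPS exclusions.
2. Add INCL04 for failures of the pre-Visit 1 regimen and dose-stability requirement that COMD04 does not catch.
3. Restore a low-compliance exclusion, using the below-80% category already derived in SAP 2.4.1.2. State that it runs only to the last dose and so does not identify early discontinuers.
4. Define what OTH04 covers.
5. If the sponsor prefers not to make any of changes 1 to 3, declare and justify that departure from protocol 9.1 in SAP section 4.

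The cost is SAP wording and a few deviation flags from data already collected. The PPS becomes slightly smaller and loses a little precision. The primary FAS analysis is untouched.
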